University of Miami - Miller School of Medicine

Set-Enhanced Aftercare for Mothers in Substance Abuse Recovery and Their Children

Version Date 6-7-2016

National Clinical Trial Number: NCT02702193

[name]

4. Description of Study

Study Protocol

4.1. * Abstract and Specific Aims

Include a brief summary of the significance, purpose or research question, specific aims, and risks/benefits. Specific aims include hypotheses you will investigate.

The study will conduct a translational randomized trial comparing an adaptation of Structural Ecosystems Therapy (SET), "Healthy Home", as an enhancement of substance abuse or mental health outpatient treatment, to outpatient treatment as usual (TAU) among approximately 172 Black, Hispanic and White non-Hispanic mothers enrolled in outpatient substance abuse, mental health or substance abuse as a co-occurring condition treatment. The study will be conducted with a community partner, Banyan Health Systems (also known as Miami Behavioral Health and Spectrum Programs), that delivers integrated substance abuse/mental health treatment and primary care. Agency staff will conduct data collection and agency nurses will deliver Healthy Home. Data will be collected at baseline and 4, 8, and 12 months post-randomization.

The Specific Aims of the proposed study are to:

- 1) test the effectiveness of SET for improving physical and mental health and reducing relapse of mothers in substance abuse/mental health recovery;
- 2) test the effectiveness of SET for improving health and mental health outcomes of children of mothers in recovery;
- 3) test mechanisms of action of SET (self care, environmental risk, family functioning and stigma);
- 4) assess SET implementation and sustainability factors and the relationship between fidelity and outcomes; and
- 5) examine the interactions of ethnicity and ethnicity-related factors on outcomes.

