Study Setting: Participant recruitment, outreach, consent and data collection, as well as the interventions, will be conducted by staff of the Banyan Health Systems (Banyan), a joint venture between Spectrum Programs, Inc. and Miami Behavioral Health Center, Inc. which joined forces 6 years ago to integrate mental health and substance abuse treatment services.

Screening, Recruitment and Retention: Study staff employed by Banyan will invite all women who are enrolled in outpatient substance abuse, mental health (or co-occurring) treatment or case management at Banyan and who have minor children to participate in the study. Study staff will also accept referrals from women receiving outpatient substance abuse, mental health (or co-occurring) treatment at other centers. Study staff will ask local agencies that serve women who receive mental health or substance abuse treatment to provide contact information for their clients who have consented to be called regarding the study. Those women will be called by study staff for recruitment to the study. The study will also be promoted via social media (e.g., Craigslist); potential participants will be instructed to call the study number - there will be no direct communication with individual study candidates via social media. For purposes of participant recruitment and retention, communication with participants includes email and text messages. The body of the messages will not include any mentions of private health information. Participants also receive greeting cards (e.g., mother's day, birthday, holiday) from the study team.

After the baseline assessment, the mother will be given a postcard indicating her treatment conditions (uploaded in section 6.2a). Staff will call enrolled women monthly to check in regarding plans to relocate, changes in contact information and to remind them of their next assessment appointment. Mothers who are unavailable for in-person assessments (e.g., if they have relocated out of town) may have their assessments by phone.

Pilot Phase: There will be a period used for piloting, refining and manualizing procedures, training the study team, translation of materials to Spanish as needed, and to apply for a Certificate of Confidentiality. The research procedures including recruiting, screening, consenting/assenting and data collection will be pilot tested with up to four sets of mothers and children at up to two time-points. [This portion of the study has been completed].

Measures:

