- Family Functioning will be measured with the family cohesion subscale of the Family Environment Scale (Moos & Moos, 1981). Family Coping will be measured with two subscales from the Family-Crisis Oriented Evaluation Scales (F-COPES; McCubbin, Larsen, & Olsen, 1996).
- Social Support will be assessed using the Important People Interview (Clifford & Langabuagh, 1991).
- Stigma will be measured using a version of a Stigma scale (Ahern, Stuber, & Galea, 2007).
- Maternal Parenting Functioning will be assessed using the Parenting Practices Questionnaire (Gorman-Smith, Tolan, Zelli, & Huesmann, 1996) and Parenting Self Agency (Dumka, Stoerzinger, Jackson & Roosa; 1996) .

Moderator Measures

- Ethnicity (Black, Hispanic, White non-Hispanic), Socio-economic Status and general demographic information will be collected using demographics items from El Centro and other UM IRB-approved studies.
- Household Composition and Stability will be collected using a Household Composition Form.
- Mother's Stress will be assessed using the Hassles Scale (DeLongis, Folkman, & Lazarus, 1988)
- Mother's Abuse and History of Abuse will be measured using the Violence Scale (Peragallo, 2005).
- Mother's Sleep will be assessed with 4 items regarding sleep from the PROMIS-29 Health Scale.

We will be extracting some information from our intervention clinical forms to capture some of our research constructs. This information includes data related to health assessments, recommendations/referrals, treatment/services rendered, follow-up plan of care, and education. The data collection form has been created in RedCap (Research electronic data capture), an electronic data capture software. A table demonstrating items extracted from the clinical forms is uploaded to the eprost protocol. These clinical forms are kept in the locked research vault at the School of Nursing and Health Studies and will be protected at all times. RedCap data will be kept in password protected files.

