The three basic techniques in SET are joining, structural diagnosis, and restructuring. Joining refers to the process of establishing therapeutic alliances. Diagnosing refers to the identification of interactional patterns that contribute to the problems experienced by the mother, and thus need to be changed, as well as those that are sources of support and thus should be reinforced. Restructuring involves orchestrating opportunities for individuals to interact in ways that reinforce strengths and change maladaptive interactional patterns. Each Healthy Home case is tailored to the particular needs of the mother and her family. Healthy Home consists of three phases of treatment: initiation, treatment, and termination. Specific focus areas include: Substance abuse contexts, support and family status, couple relationships, parenting, and health/self-care. Healthy Home training will be conducted by [name] and another trainer. Healthy Home supervision will be ongoing and conducted by [name] and Banyan clinical supervisors.

-TAU consists of substance abuse outpatient treatment services normally offered by Banyan and other agencies where the women are receiving substance abuse or mental health services.

In addition to collecting measures from mothers and children, staff of the Banyan Health System will complete measures for assessment of study implementation factors. We do not believe that these measures constitute human subjects research and therefore do not consider

staff to be study participants. Measures are as follows:

- Healthy Home Treatment Fidelity. Healthy Home nurses will typically complete a fidelity checklist after each family visit.
- Implementation Costs will be obtained from invoices completed by agency administrators that cover the full range of costs involved in implementing Healthy Home, salaries (training, supervision, and delivery), materials, etc. Nurses will log all contacts with participants (phone calls, visits, time/location, purpose, etc.). Nurses will log the amount of time spent each week on cases that does not involve contact with participants, e.g., documentation, preparation, discussing cases with colleagues, training, etc.
- Satisfaction with Implementation will be assessed using a measure adapted from a previous substance use intervention study (Santisteban, 2008). Nurses, supervisors and agency administrators will rate their satisfaction with training, supervision, intervention, and impact on delivery of usual services.

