4.4.A. Standard Measures: Click the "Add" button to open the search window, then click the "Find" button to browse and select measures.

Name of Measure	Brief Description	Type of Measure
There are no items to display		

NOTE: A copy of the first page of each standard measure is provided in the [Library of Standard Measures](#) for verification. Ensure that the version being used in this study is the same as the version that has been selected.

Upload any questionnaires and/or assessment tools to be used that are not listed above:

Name	Description Version
Child Behavior Checklist Preschool CBCP.040813.docx	0.01
Child Behavior Checklist Schoolage CBCS.040813.docx	0.01
CHILD DEMOGRAPHIC INTAKE FORM CDIM.docx	0.03
Child Health Questionnaire Physical and Fam Scales Child Report CHQC.041013.docx	0.01
Child Health Questionnaire Physical CG and Family Scales Mother Report CHQM. 041013.docx	0.01
Child's BMI BMIC.040913.docx	0.01
Family Environment Scale Cohesion FES.040913.docx	0.01
FCO FCOPES bilingual.docx	0.01
FI Dental Care Study Child Rating FDSC.040813.docx	0.01
FL Dental Care Study Mother Rating Child FDSM.040813.docx	0.01
FL Dental Care Study Mother rating herself FDSW.040813.docx	0.01
Healthy Home Hassles Scale (HHH).docx	0.01
Healthy Home Important People Interview (IPI) English.docx	0.01
Healthy Home Important People Interview (IPI) Spanish.docx	0.01
HLF Health Literacy Screener HLF.041513.docx	0.01
Household Composition Form HCF.040913.docx	0.01

MDIF Mother Demographic-Translation v2.doc	0.05
Measures_Table_for IRB protocol.04-16-2013.docx	0.01
Modified Stigma Scale with Alcohol MSS.040913.docx	0.02
MSF (Mother Screening Form) with mental health.010914.	0.01
Oral Health Impact Scale Mother rating self OHIP.040913.docx	0.01
Pap Smear Last Check Form LCF.040913.docx	0.01
Parenting Practices Child Report PPC.041013.docx	0.01
Parenting Practices Parent Report PPP.040813.docx	0.01
Parenting Self Agency PSA.040813.docx	0.01
PER--Parent Relationship With Peer Group-Parent (English).doc	0.01
PER--Parent Relationship With Peer Group-Parent (Espanol) (DD).doc	0.01
PROMIS SF v1.0 - ED-Anxiety-SF8a Spanish.pdf	0.01
PROMIS SF v1.0 - ED-Anxiety-SF8a.pdf	0.01
PROMIS SF v1.0 - ED-Depression-SF8a Spanish.pdf	0.01
PROMIS SF v1.0 - ED-Depression-SF8a.pdf	0.01
SET-R Addiction Severity Index LITE (ASI).RX accomodation.docx	0.01
SET-R Form 90 (F90).doc	0.01
SET-R PROMIS 29 Profile ENGLISH.docx	0.01
SET-R PROMIS 29 Profile SPANISH.docx	0.01

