To be eligible for the study Mothers must meet all of the following criteria: (1) Enrolled in outpatient substance abuse or mental health treatment (or treatment for substance abuse as a co-occurring disorder) or case management for mental health or substance abuse problems, (2) have at least one child age 0-17 with whom she has at least monthly contact (3) be age 18 or above, (4) capable of giving informed consent and comprehending either English or Spanish, (5) willing and able to participate fully in the protocol (e.g., to accept assignment to either condition, to provide sufficient locator information for follow-up, to allow their treatment sessions to be monitored for fidelity/process assessment and supervision).

To be eligible for the study Children must meet all of the following criteria: (1) biological, step or adopted child of a mother enrolled in the study and with whom the mother has at least monthly contact (2) age 2-17, (3) has the signed permission of a legal guardian to enroll in the study, (4) gives assent to participate in the study if age 7 or above.

5.8. * Will only one group of individuals be systematically selected and recruited for this study (e.g., welfare patients, racial and/or ethnic minorities, persons confined to institutions or persons determined to be incapacitated)?

Yes No

5.8.A. If yes, please state how this participant group will benefit from the results of the research and provide the reasons and justifications to target this group:

This study focuses on women in substance abuse/mental health treatment and their children. These groups are at high risk for significant health consequences and there is a need for culturally-informed interventions tailored to address their unique needs.

5c. Research Involving Pregnant Women or Fetuses

Pregnant woman or fetuses may be involved in research if **ALL** of the following conditions are met (all items must be justified):

(a) **Where scientifically appropriate, preclinical studies, including studies on pregnant animals, and clinical studies, including studies on nonpregnant women, have been conducted and provide data for assessing potential risks to pregnant women and fetuses.**

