Mothers will be recruited from substance abuse/mental health treatment sites run by Banyan. Study staff employed by Banyan will invite all women who are enrolled in outpatient substance abuse, mental health (or co-occurring) treatment and who have children ages 0-17 to participate in the study. Study staff will contact candidates up to 4 times to offer study enrollment. Candidates who express interest in participating will be administered a screening interview by phone or in person. Study staff will explain the study and if the mother agrees to participate she will be read and asked to provide signed consent and permission for her children to participate.

In addition, study personnel will reach out to personnel from sites that refer women to Banyan for outpatient substance abuse or mental health treatment. This includes Banyan-affiliated residential substance abuse treatment sites, Family Intervention Services, the drug courts and other venues. The study team members will talk to personnel of those sites about the study and

provide them with IRB-approved study flyers and pamphlets and ask them to distribute these materials to mothers who might be referred to Banyan for outpatient substance abuse treatment. Study staff will ask local agencies that serve women who receive mental health or substance abuse treatment to provide contact information for their clients who have consented to be called regarding the study. Those women will be called by study staff for recruitment to the study. We will also use social media (e.g., Craigslist) to broadcast information about the study as a means of promoting recruitment. Potential participants will have to call the study number - there will be no direct communication with individual study candidates via social media.

In addition, the study will accept self-referrals from women who are receiving substance abuse, mental health (or co-occurring) treatment at other centers (besides Banyan). Study staff will inform staff at substance abuse/mental health treatment center about the study and will provide them with flyers and pamphlets. Staff from the substance abuse/mental health treatment center will post/distribute flyers/pamphlets and those clients who are interested will contact the study.

After obtaining the mother's informed consent to enroll in the study, study staff will administer the Child ID Form to identify children who are eligible to participate.

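### Treatment track and treating agency shape usual care and are fixed before randomisation, yet neither is a pre-specified covariate or a listed moderator, so precision may be lost and a benefit confined to one track would show only as a diluted average

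*Combined protocol and SAP*

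**What the plan says.** **Who is enrolled.** Section 4.1 plans the comparison "among approximately 172 Black, Hispanic and White non-Hispanic mothers enrolled in outpatient substance abuse, mental health or substance abuse as a co-occurring condition treatment". The first criterion for mothers in section 5.7 is wider: "Enrolled in outpatient substance abuse or mental health treatment (or treatment for substance abuse as a co-occurring disorder) or case management". On agency, section 4.4 (Screening, Recruitment and Retention) adds: "Study staff will also accept referrals from women receiving outpatient substance abuse, mental health (or co-occurring) treatment at other centers". Section 6.2 repeats this for self-referrals.

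**What the control is.** Section 4.4 (Interventions) says "TAU consists of substance abuse outpatient treatment services normally offered by Banyan and other agencies"; the rest of that sentence refers to the places where the women receive substance abuse or mental health services. Section 4.5 describes TAU as the substance abuse, mental health or co-occurring treatment that the mother's own programme routinely provides. Neither description mentions case management.

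**How outcomes are analysed.** Section 4.12 fits latent growth models in which condition predicts the trajectory. It has two adjustment rules, both triggered by observed imbalance. Under the randomisation check, variables judged theoretically relevant to the outcome are controlled if they differ by condition. Under the hypothesis tests, socio-demographic variables and pretest outcome levels can be controlled if they differ by arm.

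**Moderators.** Section 4.4 (Moderator Measures) lists ethnicity, household composition, stress, abuse and sleep, and says "Socio-economic Status and general demographic information will be collected using demographics items". Section 4.12 uses the proposed moderators for exploratory interactions with treatment. Track and agency are not among them.

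**The concern.** A control mother receives whatever her programme offers, so the contrast between Healthy Home plus TAU and TAU alone is not the same contrast for every mother. Enrolment in treatment or case management is an entry criterion, and section 4.4 places randomisation after baseline. Track and agency are therefore baseline facts that could safely be used in the analysis.

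Two things are at stake. First, if track or agency predicts change in an outcome, leaving it out of a linear model leaves that variation in the error term. A rule triggered by imbalance does not recover it when the arms happen to be balanced. Second, the effect may plausibly differ by track. Section 4.4 describes Healthy Home as built for women being treated for substance abuse: the nurse liaises with the substance abuse counsellor, and substance abuse contexts are a focus area. Aim 1 includes reducing relapse. A mother treated only for mental health may have little room to improve on that outcome. No planned analysis would show that a modest average was made up of a benefit in one track and none in another.

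**Working it through.** **Inputs from the documents.** About 172 mothers (section 4.1). Not given: alpha, power, planning effect, SD, dropout rate, allocation ratio, and the shares of mothers by track or agency. The figure of 172 therefore cannot be reproduced.

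**Assumptions.** 1:1 allocation (86 per arm), two-sided 0.05, outcome SD 1, no dropout, normal approximation, one continuous contrast.

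**Benchmark.** SE = sqrt(2/86) = 0.1525. The effect detectable with 80% power is (1.960 + 0.842) x 0.1525 = 0.43 SD. Power is about 75% at 0.40 SD and 91% at 0.50 SD.

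**Precision.** If the omitted factors explain a share R2 of the relevant variance, the SE is inflated by 1/sqrt(1 - R2), and adjusting is worth a total of 172/(1 - R2) mothers.

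| R2 (assumed) | SE inflation | Equivalent N | Power at 0.40 SD after adjusting (74.6% before) |
|---|---|---|---|
| 2% | 1.0% | 176 | 75.5% |
| 5% | 2.6% | 181 | 76.8% |
| 10% | 5.4% | 191 | 79.0% |
| 20% | 11.8% | 215 | 83.5% |

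For a test on the slope, the relevant R2 is the share of variation in change. Stable level differences between tracks go into the latent intercept, so a large gap in level does not imply a large gain.

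**Dilution.** Average effect = p x (effect in one track) + (1 - p) x (effect in the rest).

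- 0.5 and 0, p = 0.5: average 0.25; power 37%, against 91% if the effect were uniform.
- 0.5 and 0, p = 0.7: average 0.35; power 63%.
- 0.40 and 0, p = 0.6: average 0.24; power = Phi(0.24/0.1525 - 1.960) = Phi(-0.39), about 35%, against 75%.

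**What an interaction could show.** With n1 and n2 mothers per arm in the two tracks, SE = sqrt(2/n1 + 2/n2).

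- 50/50 (43 and 43): SE = 0.305; 80% power needs a between-track difference of 2.802 x 0.305 = 0.85 SD; 95% CI half-width 1.96 x 0.305 = 0.60 SD.
- 70/30 (60.2 and 25.8): SE = 0.333; 0.93 SD needed; half-width 0.65 SD.
- For 0.40 against 0 at 60/40: SE = sqrt(2/51.6 + 2/34.4) = 0.311; power = Phi(0.40/0.311 - 1.960), about 25%.

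**Does anything else in the plan fill the gap?** Section 4.4 (Interventions) tracks Healthy Home and substance abuse services to compare exposure between arms. That is description by arm. It does not adjust the outcome models or estimate the effect by track.

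**The case against.** The strongest reply has five parts.

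- **The TAU sentence is loose rather than wrong.** A reader who stops at the words quoted from section 4.4 might infer that the control is defined as substance abuse services only. The sentence goes on to cover women receiving mental health services, and section 4.5 and the study design paragraph of 4.4 include mental health and co-occurring treatment. What stands is a wording mismatch and the silence on case management.
- **The tracks may overlap.** Section 4.1 describes Banyan as delivering integrated care, and section 4.2 reports a mental health diagnosis in 68% of women at the substance abuse treatment agency. This stands, and it favours a coarse grouping.
- **The first adjustment rule could admit track or agency.** So it could, if the arms differed and the factor were judged relevant. But it names neither factor, recovers no precision when the arms are balanced, and does not estimate heterogeneity.
- **The precision gain is speculative.** This stands. The documents do not show that track strongly predicts change, least of all for child outcomes. For binary outcomes analysed on the logit scale, covariate adjustment typically increases the SE of the log odds ratio, so the table above does not carry over.
- **The interaction would rarely be conclusive.** This also stands, and is why estimates with intervals are proposed rather than tests.

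A reader might also infer that effects in opposite directions are being averaged away, or that the pooled estimate is biased. Nothing in the documents suggests opposite effects; a benefit in one track and little in another is the supportable scenario. Randomisation keeps the pooled contrast unbiased whether or not these factors are modelled.

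**Conclusion.** The point holds as one of efficiency and interpretation, not validity. Usual care depends on two factors fixed before randomisation, and the plan neither commits to adjusting for them nor lists them as moderators. The precision cost is probably small to moderate: about 1-12% of the SE if the factors explain 2-20% of the relevant variance, and less where the latent intercept already carries level differences. The dilution cost could be larger. In the illustrations, power falls from 91% to 37%, or from 75% to 35%, but track shares and track-specific effects are assumed throughout. At this size the trial could reliably detect only between-track differences of about 0.85-0.93 SD, so any result by track or agency would be exploratory.

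**What to change.** 1. Enter treatment track and agency (Banyan versus other), as recorded at enrolment, as covariates in the Aim 1 and Aim 2 growth models regardless of balance. State in advance how sparse track categories will be collapsed, for example any substance abuse treatment versus mental health only.
2. Add both to the exploratory moderators. Report condition-by-track and condition-by-agency estimates with confidence intervals rather than tests.
3. Reconcile the TAU wording in section 4.4 (Interventions) with section 4.5 and with the eligibility rule in section 5.7.

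**Cost.** Mainly SAP wording. Four track categories (3 parameters) plus agency (1) add 3 + 1 = 4 parameters per growth factor, or 8 for intercept and slope, before interactions. With track collapsed to two groups this is 2 per growth factor, or 4 in all. One practical check is needed. The uploaded tools in section 4.4.A include "MSF (Mother Screening Form) with mental health", but its content is not shown, and the screening questions given as examples in section 7.8.A are age, minor children and monthly contact. The team should confirm that track and agency can be taken from enrolment records for every mother.
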